Aim 1A: On the day of surgery, patients will be asked about paresthesia and loss of sensation around the umbilicus. We will document the time when normal sensation returns following the administration of the block. The time elapsed (in minutes) between rectus sheath blockade and the point at which normal sensation returns will be compared between the groups.

Aim 1B: Every 2 hours, we will question the patients regarding their need for pain medication and obtain their Numeric Rating Scale (NRS) pain scores for umbilicus incisional pain. We will document when the patient needs pain medication. The time elapsed (in minutes) from the rectus sheath blockade until the first request for umbilicus pain medication, as well as NRS pain scores will be compared between groups.

Hypothesis:

We hypothesize that rectus sheath injections with the ropivacaine/clonidine combination will be superior in providing long lasting analgesia compared to ropivacaine alone, increasing the duration of sensory block and analgesia, and lowering pain scores at the umbilicus incision.

Aim 2. We will determine if any improvements we observe in pain control satisfaction with the ropivacaine/clonidine combination can be attributed to clonidine's ability to reduce anxiety.

Aim 2A will compare between the two groups patient, parent, and nurse NRS satisfaction scores and correlate them with post-op scores on the state-anxiety component of the State-Trait Anxiety Inventory for Children (STAIC S – Anxiety). Aim 2B will compare postoperative

STAIC S – Anxiety scores between the two groups. Aim 2C will compare within the two groups the difference between the pre and post- op STAIC S Anxiety scores to show if ropivacaine/clonidine is more effective at reducing anxiety.

The methodology will be the following:

Aim 2A: NRS pain control satisfaction scores from patient, parent and nurse will be collected at the completion of the study. State-Trait Anxiety Inventory for Children (STAIC S – Anxiety) questionnaires will be administered to both groups before surgery, and at hour 6 after rectus sheath injections. Post-op anxiety scores in each group will be correlated with satisfaction scores. Aim 2B: The postoperative STAIC S – Anxiety scores will be compared between the 2 groups. Aim 2C: The pre-op STAIC S Anxiety scores will be compared with post- op STAIC S Anxiety within each group.

Hypothesis:

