We hypothesize that patients, parents and nurses will experience more pain control satisfaction with the ropivacaine/clonidine combination than with the ropivacaine alone, not only because the combination will provide longer lasting analgesia, but also because clonidine's power to reduce anxiety will lead to a concomitant decrease in pain.

C. BACKGROUND

Appendectomy is one of the most common emergency surgeries performed in children, especially in adolescents and teens. (1) At present, the laparoscopic technique has become a popular approach for performing appendectomies, (1) as it is minimally invasive and has been shown to improve patients' outcomes. (2). Despite these advantages, children often experience significant pain (3) and anxiety during these laparoscopic procedures that extends after the day of surgery, particularly those who are particularly anxious before surgery. Indeed, children who are highly anxious prior to surgery tend to have more postoperative pain, delayed hospital discharge, higher incidence of emergence delirium, sleep disturbances, and other maladaptive behavior changes that can last up to a few weeks following surgery. (4), (5)

Effective postoperative analgesia after laparoscopic appendectomy is necessary for optimal recovery. (3) By simultaneously improving analgesia and reducing side-effects from opioid use, a multimodal approach that includes peripheral nerve blocks—a form of regional analgesia—could form the crux of an effective pain control regimen for patients undergoing laparoscopic appendectomy. Despite the promise of such an approach, finding a nerve block that is suitable for patients undergoing laparoscopic appendectomies is challenging. Nerve blocks typically consist of local anesthetic alone, and it is difficult to find a local anesthetic with both minimal side effects and ability to combat pain and anxiety for extended periods of time. For instance, even though single injection nerve blocks (such as rectus sheath blocks) in combination with multimodal analgesia for laparoscopic appendectomy are helpful and minimally invasive, they do not last over the course of the most painful part of postoperative period, the first 24 hours. (6) By contrast, continuous peripheral nerve blocks can provide enduring analgesia, but they are costly and deemed excessively invasive in the context of this minimally invasive surgery.

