In the operating room, standard anesthesia monitors will be connected and general anesthesia will be performed as per the anesthesiologist's standard of care. At the completion of surgery, acetaminophen iv and ketorolac will be administered by the anesthesia provider. Dexmedetomidine will not be administered during anesthesia or after the completion of anesthesia. A member of CHP Acute Interventional Perioperative Pain Service (AIPPS) – attending or fellow will perform all bilateral ultrasound guided rectus sheath blocks as per CHP standard of care using the study drug. The surgeon will not infiltrate the local anesthetic at the laparoscopic instrument sites.

Postoperative Study Protocol:

For the following 24 hours, the analgesic regimen will include ketorolac every 6 hours (if not contraindicated by surgeon), acetaminophen iv every 6 hours, oxycodone by mouth as needed for pain, every 4 hours, and hydromorphone iv as needed for pain, every 2 hour.

In the postoperative period the patients will be asked to complete a few questionnaires created for this study. The nurse taking care of the patient, principal investigator, one of the co-investigators, or the research assistant will do the assessment. Starting in the PACU, the patients will be questioned about the presence of paresthesia around the umbilicus instrument site ("is the area around your belly button numb") and the umbilical pain severity using NRS scale (0 being no pain and 10 the worst imaginable pain). They will also be asked about their need for pain medication for umbilical pain as well as the amount of pain medication they have consumed for pain in that region. The assessment will continue on the floor every 2 hours until complete resolution of paresthesia at the umbilicus or until the patient is discharged home. The state version (S-anxiety) of the State-Trait Anxiety Inventory for Children (STAIC) will be administered to measure patient anxiety before surgery after the consent is done and 6 hours after rectus sheath injections. At the completion of the study,

the patient's, parent's, and nurse's satisfaction with pain control will be investigated using an NRS scale (0 being very unsatisfied and 10 being very satisfied).

E. STATISTICS: ASSESSMENT OF ADEQUACY OF SAMPLE SIZE

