Descriptive statistics will be presented as frequencies (percentages, %) for categorical data or as mean \pm standard deviation (SD) or median and interquartile range for normally or non-normally distributed continuous data, as appropriate. Examination of normal distribution assumption for continuous data will be determined by q-q plots and histograms. Two sample T-Test or Wilcoxon-Mann-Whitney test will be performed to determine differences between groups for normally or non-normally distributed continuous data, respectively. Pearson's chi-square or Fisher's exact test, as appropriate, will be used to compare the frequency distribution of categorical variables between the groups. We will compute Pearson correlation coefficient between NRS pain scores and the anxiety scores. If the assumptions for the parametric test are not met, a nonparametric alternative will be used (i.e. Spearman correlation coefficient).

Sample Size and Power:

The target sample size was calculated with the assumption that the duration of block in the group with ropivacaine only is 720 minutes \pm 288 minutes and in the group with ropivacaine and clonidine the duration is 1080 minutes \pm 432 minutes. The difference would be clinically relevant if the duration of blocks with ropivacaine and clonidine will be at least 50% or more than the duration of blocks with local anesthetic only. Assuming a power of 80%, a level of significance of 0.05, mean and SD as above, only 12 patients would be required in each group. Allowing for a 400% loss arising from patient dropout, unsuccessful block, incomplete follow up because of discharge home on the day of surgery, and inability to determine when paresthesia wears off, we plan to recruit 50 patients in each group, for a total of 100 patients. We estimate that this sample size of 100 patients would provide 80% power to detect a difference as small as 23% in the duration of paresthesia between these 2 groups.

F. SIGNIFICANCE AND APPLICABILITY

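### Umbilical pain is compared between arms without adjusting for preoperative anxiety, which the plan collects and itself links to postoperative pain; some precision may be lost

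*Combined protocol and SAP*

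**What the plan says.** All references are to the combined protocol and SAP.

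- **Predictor.** Section C (Background) says that "children who are highly anxious prior to surgery tend to have more postoperative pain".
- **Collection.** In Section B, Aim 2A, the STAIC S-Anxiety "questionnaires will be administered to both groups before surgery". Section D (Postoperative Study Protocol) gives the two time points: it is "administered to measure patient anxiety before surgery after the consent is done and 6 hours after rectus sheath injections". The first score therefore precedes the block.
- **Pain comparison.** Under Aim 1B, the time to "the first request for umbilicus pain medication, as well as NRS pain scores will be compared between groups".
- **Method.** Section E: "Two sample T-Test or Wilcoxon-Mann-Whitney test will be performed to determine differences between groups". The rest of Section E offers chi-square or Fisher tests and Pearson or Spearman correlations. It has no regression, ANCOVA or stratified test.
- **Use made of the baseline score.** Aim 2C: "The pre-op STAIC S Anxiety scores will be compared with post- op STAIC S Anxiety within each group". This concerns anxiety, within arms.
- **Allocation.** Section D (Randomization) describes a computer-generated random number table and states no stratification by anxiety.

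**The concern.** The plan names a baseline variable that it believes predicts pain, schedules its measurement before treatment in both arms, and then leaves it out of the between-arm pain analysis. No preoperative pain score is scheduled, since NRS assessment starts in the PACU. Preoperative STAIC-S is thus the only scheduled baseline score that the plan ties to postoperative pain.

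Two things are at stake. Variation in pain explained by preoperative anxiety stays in the error term, so the confidence interval for the arm difference is wider than it need be. And if the arms happen to differ in anxiety before surgery, that difference feeds into the observed pain contrast.

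The numbers analysed for pain may fall well below 50 per arm. Section D drops children discharged before paresthesia resolves from the first aim, which includes Aim 1B, and Section E plans for heavy losses.

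**Working it through.** **Inputs from the documents.** 50 recruited per arm; 12 per arm as the number required before the loss allowance; 80% power; significance level 0.05 (taken as two-sided). I use 12 per arm as a pessimistic illustration, not a forecast.

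**Input not in the documents.** The correlation r between preoperative STAIC-S and postoperative NRS pain. I assume 0.1 to 0.5.

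**The plan's own figure.** Section E gives no power for pain. Its power statement concerns duration of paresthesia: 23% detectable at 50 per group. A two-sided t-test at 50 per arm has 80% power for 0.566 SD. With the control-arm SD of 288 min and mean of 720 min, 0.566 × 288 / 720 = 22.6%, which agrees. (This match uses 288 min in both arms and sets aside the 432 min stated for the clonidine arm; that is a separate matter.) I take 0.566 SD as the reference effect for pain at 50 per arm. At 12 per arm the corresponding effect is 1.197 SD.

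**Precision.** Relative to the unadjusted analysis, the variance of the adjusted arm difference is

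(1 − r²) × (1 + 1/(2n − 4)), with 2n − 3 degrees of freedom.

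The second term is the price of estimating the covariate slope: 1 + 1/96 = 1.010 at n = 50 and 1 + 1/20 = 1.05 at n = 12. Equivalent n is n divided by the variance factor. Power is from the noncentral t distribution.

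| r | Factor, n = 50 | Equivalent n | Power | Factor, n = 12 | Equivalent n | Power |
|---|---|---|---|---|---|---|
| 0.1 | 1.000 | 50.0 | 80.0% | 1.040 | 11.5 | 78.3% |
| 0.2 | 0.970 | 51.5 | 81.2% | 1.008 | 11.9 | 79.5% |
| 0.3 | 0.919 | 54.4 | 83.2% | 0.956 | 12.6 | 81.6% |
| 0.4 | 0.849 | 58.9 | 86.0% | 0.882 | 13.6 | 84.5% |
| 0.5 | 0.758 | 66.0 | 89.6% | 0.788 | 15.2 | 88.3% |

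The variance breaks even where r² = 1 − 1/(1 + 1/(2n − 4)). This gives r of about 0.10 at 50 per arm and about 0.22 at 12 per arm.

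**Chance imbalance.** The standardised arm difference in baseline anxiety has SD √(2/n): √(2/50) = 0.20 and √(2/12) = 0.41. The probability that it exceeds 0.3 SD in either direction is 13% at 50 per arm and 46% at 12 per arm. A difference of one such SD moves the unadjusted pain contrast by r × √(2/n). At r = 0.3 that is 0.06 SD of pain at 50 per arm and 0.12 SD at 12 per arm; at r = 0.5 it is 0.10 and 0.20.

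**The case against.** **The unadjusted tests are not wrong.** A reader might infer that they are biased or have an inflated type I error. They are not: under randomisation, chance imbalance is already reflected in their standard error. For a study that calls itself a pilot, a simple two-sample test is defensible. This stands, and it limits the point to efficiency and robustness.

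**The gain cannot be read from the documents.** It is tempting to square the 0.539 in Section C (Preliminary studies) and claim a 29% variance reduction. That coefficient relates postoperative pain to postoperative anxiety, so it does not supply r for a preoperative covariate. It is also tempting to quote 1/(1 − r²), which gives 4% to 33% more patients for r of 0.2 to 0.5. That omits the finite-sample cost: the equivalent gain is about 3% to 32% at 50 per arm and runs from a slight loss to about 27% at 12 per arm.

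**The link is stated for pain only.** A reader might extend the point to every Aim 1B and Aim 2A comparison. Section C says nothing about preoperative anxiety and time to first request, or about patient, parent or nurse satisfaction; for satisfaction the link can only be inferred. For time to first request the r² argument fails as well, because adjusting a hazard ratio need not narrow its interval.

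**Section G already addresses baseline anxiety.** It does so for carry-over into postoperative anxiety scores, and relies on comparing scores before and after surgery. That does not adjust the between-arm pain contrast, so this objection falls.

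**Adjustment is not wholly free.** The score is planned for all children, but the eligibility criteria ask only for complete postoperative questionnaires, so some baseline scores may be missing. This stands and belongs in the fix. Section G also treats pain scores as open to misclassification and prefers paresthesia as the indicator of analgesia, which lowers the consequence.

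**Conclusion.** The point holds as an optional improvement to the analysis of umbilical NRS pain. The plan leaves unused a pre-treatment covariate that it collects and itself links to pain. At 50 per arm the gain over 80% power is nil at r = 0.1, about 1 point at 0.2, 3 points at 0.3 and 10 points at 0.5. With groups as small as 12 per arm, adjustment loses 0.5 to 2 points for r of 0.2 down to 0.1 and gains above that.

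These figures rest on an assumed r, a linear relation with a common slope in both arms, complete baseline scores and a two-sided 5% test. They do not show that the planned test is invalid, and they say nothing about duration of paresthesia, the outcome on which the trial is powered. Nor would adjustment repair the exclusions made after randomisation.

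**What to change.** In Section E, before unblinding:

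1. Analyse umbilical NRS pain by linear regression on arm with preoperative STAIC-S as covariate. Use one prespecified summary per child over a time window common to both arms. The common window matters because Section D stops the 2-hourly assessments when paresthesia resolves, which the treatment is expected to delay.
2. Keep the unadjusted t or Wilcoxon test as a sensitivity analysis. This also covers the bounded 0–10 scale.
3. State how a missing preoperative STAIC-S will be handled, so that no child is dropped for lack of a covariate.
4. Do not use the 6-hour STAIC-S as the covariate; treatment may affect it.
5. The same model may be used for the satisfaction scores, with a note that the link to preoperative anxiety is inferred there.
6. Make no precision claim for time to first request. Any adjusted analysis of it needs a named time-to-event model that censors children who make no request.

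The cost is SAP wording, one degree of freedom, the missing-data rule, and a possible slight loss of power if both r and the analysed groups are small. No new data item is needed for the covariate.

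### The sample-size figures do not follow from the stated SDs: 12 per group gives about 63% power, not 80%, and the 23% detectable difference needs an SD of 288 in both groups and no loss.

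*Combined protocol and SAP*

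**What the plan says.** The whole sample-size justification is one paragraph, in section E under Sample Size and Power.

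- **Control group:** "the duration of block in the group with ropivacaine only is 720 minutes", with an SD of 288.
- **Clonidine group:** "ropivacaine and clonidine the duration is 1080 minutes", with an SD of 432.
- **Relevant effect:** a duration at least 50% longer than with local anesthetic alone, which is 360 minutes.
- **Error rates:** "Assuming a power of 80%, a level of significance of 0.05". Sidedness is not given.
- **Required number:** "mean and SD as above, only 12 patients would be required in each group".
- **Inflation:** "Allowing for a 400% loss arising from patient dropout, unsuccessful block", and other causes, leading to 50 recruited per group.
- **Detectable difference:** "this sample size of 100 patients would provide 80% power to detect a difference as small as 23% in the duration of paresthesia". The SD behind this figure is not stated.

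The opening paragraph of section E names the two-sample t-test, or Wilcoxon-Mann-Whitney if the data are not normal, for comparing continuous outcomes. In section D, Patient eligibility removes failed blocks, conversions to open surgery, patients who cannot time the return of sensation to within an hour, and patients with no follow-up. For the first aim it also removes anyone discharged before the paresthesia resolves.

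**The concern.** The paragraph gives a separate SD for each group and says the required number uses them, but 12 per group is too few for SDs of 288 and 432. The 23% looks too small for the same reason. It also relies on all 100 patients, directly after a sentence that allows for loss down to about 12 per group. A loss above 100% has no literal meaning.

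Two readings of the trial are at risk. Anyone tracking attrition against a floor of 12 per group would accept a 76% loss in the belief that power was still 80%. Anyone reading a null result against the 23% figure could rule out differences that the trial had no good chance of detecting.

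**Working it through.** **Inputs (all from section E).** Means 720 and 1080, so the difference is 360 minutes; SDs 288 and 432; level 0.05; power 80%; equal groups; two-sample t-test. Two-sided testing is assumed, since the plan speaks only of differences between groups.

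**Formulas.** The standard error with n per group is SE = √[(SD₁² + SD₂²)/n]. The noncentrality is δ = 360/SE. Power is the probability that a noncentral t variable with noncentrality δ exceeds the two-sided critical value.

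**1. Reproducing the plan's 12 and 23%.** Put SD 288 in both groups.

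- n = 11 gives 79.6% power and n = 12 gives 83.3%, so the required number is 12.
- With 50 per group, SE = 288 × √(2/50) = 57.6. The difference with 80% power is 163.0 minutes, and 163.0/720 = 22.6%, which rounds to 23%.

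One substitution therefore yields both published figures, and the second also needs all 50 per group to be analysed.

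**2. Required number with the stated SDs.** 288² + 432² = 269,568.

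- Normal approximation: n = (1.960 + 0.842)² × 269,568/360² = 7.849 × 2.08 = 16.3, so 17.
- At n = 12: SE = √(269,568/12) = 149.9 and δ = 2.40, against a critical value of 2.07 on 22 df.
- At n = 18: SE = 122.4 and δ = 2.94, against 2.03 on 34 df.

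| n per group | Pooled t | Welch |
|---|---|---|
| 12 | 63.2% | 62.6% |
| 17 | 79.2% | 78.8% |
| 18 | 81.5% | 81.2% |

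So 18 per group are needed. Simulation at n = 12 agrees (63.2% pooled, 62.2% Welch), and the Wilcoxon test gives about 58.5%.

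**3. Detectable difference at 80% power, as a percentage of 720.** The second column keeps SDs 288 and 432. The third lets the clonidine SD scale with its mean, because both stated pairs have a coefficient of variation (CV) of 0.40 (288/720 = 432/1080).

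| Evaluable per group | SDs 288 and 432 | CV 0.40 |
|---|---|---|
| 50 | 208 min (29%) | 185 min (26%) |
| 18 | 353–354 min (49%) | 351–353 min (49%) |
| 12 | 439–442 min (61%) | 471–478 min (65–66%) |

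Ranges run from pooled to Welch. For a true 23% difference (0.23 × 720 = 165.6 minutes) with 50 per group and no loss, power is 61% with the stated SDs and 72% with CV 0.40.

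**4. The loss allowance.** From 50 to 12 is 38/50 = 76%. The wording probably means fourfold inflation: 12 × 4 = 48, rounded to 50. Keeping the 18 actually needed tolerates 32/50 = 64%.

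**5. Other readings of the inputs.**

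| Reading | n for 80% power | Detectable at 50 per group |
|---|---|---|
| One-sided t, stated SDs | 14 | 25.5% |
| Two-sided log scale, CV 0.40 | 16 | 24.4% |
| One-sided log scale, CV 0.40 | 12 (80.3% power) | 21.3% |
| Two-sided t, SD 288 in both groups | 12 (83.3% power) | 22.6% |

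Of these, only the last gives both published figures, and it drops the stated 432.

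**The case against.** The strongest reply is that the error does little harm to the trial as sized. Fifty per group is nearly three times the correct 18. With 25 evaluable per group, power for the 50% effect is still about 92%, and only a loss above 64% takes it below 80%. The plan allows for heavy loss without forecasting it, and the study calls itself a pilot. This stands, and it is why no increase in size is asked for. It does not make the printed figures right.

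Second, a worst-case allowance and a full-sample sensitivity statement can sit side by side. That is fair: the plan never says that only 12 per group will be evaluable. But the 23% sentence states neither its no-loss condition nor its SD, and the exclusions in section D mean some loss is to be expected. Even with no loss, 23% is too low for the stated SDs.

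Third, 12 alone can also come from a one-sided test on the log scale. This too is correct, so 288 in both groups is not the only route to 12. The plan mentions neither a log scale nor a one-sided test, however, and that route does not give 23%.

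Finally, the 400% is loose wording for inflation, and the required number and the detectable difference probably share one slip. Both points are accepted; all the affected sentences still need correcting.

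**Conclusion.** The concern holds. For SDs of 288 and 432, a two-sided 0.05 t-test needs 18 evaluable patients per group, half as many again as the stated 12, at which power is about 63%. The detectable difference with all 100 evaluable is about 29%, or about 26% under a constant CV, rather than 23%. If loss went as far as the inflation implies, leaving 12 per group, the detectable difference would be 61% to 66%, above the 50% effect the plan is built on. Both errors flatter the trial.

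The conclusion rests on two-sided testing, which the plan does not state, and on taking its two SDs at face value. A one-sided test with the same SDs would still need 14. The planned total of 100 remains adequate for the 50% effect if loss stays at or below 64%.

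**What to change.** Correct the paragraph in section E and leave the total at 100.

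- State that the test is two-sided at 0.05.
- Replace 12 with 18 evaluable per group, for 80% power with SDs 288 and 432.
- Replace the 400% loss by the statement that 50 randomised per group tolerates up to 64% loss (18 of 50 kept).
- Replace the 23% sentence with a detectable difference of about 29% if all 100 are evaluable and about 50% at 18 evaluable per group, naming the SDs used. If the SD is meant to scale with the mean, say so and give about 26% for the no-loss case.

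The cost is a text correction only. No patients are added and no procedure changes; the stated figures become less favourable.
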